10.3 Study Termination

Although ITI has every intention of completing the study, ITI reserves the right to discontinue the study at any time for clinical or administrative reasons.

The end of the study is defined as the date on which the last patient completes the last visit (includes follow-up visit).

**MODIFICATION HISTORY**

Unique Identifier for this Version	Date of the Document Version	Author	Significant Changes from Previous Authorized Version
1.0	16Mar2016	[REDACTED]	Not Applicable – First Version
1.1	19Dec2017	[REDACTED]	Text added to describe the planned interim analysis as well as the tipping point sensitivity analysis. In addition, updates required following review of V1.0 were implemented.
1.2	22Feb2018	[REDACTED]	Update to address sponsor comments
1.3	30Apr2018	[REDACTED]	Update for protocol amendment
2.0	09Jul2018	[REDACTED]	Update for correction in conditional power formula in Appendix 4
3.0	12Jul2018	[REDACTED]	Update for correction to effect size calculation
4.0	12Jun2019	[REDACTED]	Update for additional analyses, sponsor comments on dry runs, and minor corrections

## 1. LIST OF ABBREVIATIONS

AE	Adverse Event
AIMS	Abnormal Involuntary Movement Scale
ANCOVA	Analysis of Covariance
AR(1)	Autoregressive(1)
ARH(1)	Heterogeneous autoregressive(1)
BARS	Barnes Akathisia Rating Scale
BLQ	Below the limit of quantification
BMI	Body mass index
BPI	Bipolarity Index
C-SSRS	Columbia – Suicide Severity Rating Scale
CGI-BP-S	Clinical Global Impression Scale, Bipolar Version – Severity
CI	Confidence interval
CPK	Creatine phosphokinase
C-VISA™	Clinical Validation Inventory for Study Admission (Bracket)
DMC	Data Monitoring Committee
DSM-V	Diagnostic and Statistical Manual, Fifth Edition
ECG	Electrocardiogram
eCRF	Electronic Case Report Form
ENR	All Subjects Enrolled
EPS	Extrapyramidal symptoms
FAO(q)	No diagonal factor analytic
FWER	Familywise error rate
GGT	Gamma-glutamyl transferase
HIV	human immunodeficiency virus
HR	Heart rate
IEC	Independent Ethics Committee
IRB	Institutional Review Board
ITCI	Intra-Cellular Therapies, Inc. (Sponsor)
ITT	Intent-to-Treat
LOCF	Last observation carried forward
LOE	Lack of efficacy
LS	Least squares
MADRS	Montgomery-Åsberg Depression Rating Scale
MAR	Missing at random
MedDRA	Medical Dictionary for Regulatory Activities
MI	Multiple imputation
MMRM	Mixed-Effect Model Repeated Measure
MNAR	Missing not at random
NEO-FFI	Neuroticism, Extraversion and Openness to Experience - Five Factor Inventory
OLE	Open label extension
PR	PR interval of the electrocardiogram; time duration between the P and R waves
PT	Preferred Term
Q-LES-Q-SF	Quality of Life Enjoyment and Satisfaction Questionnaire – Short Form

QRS	QRS interval of the electrocardiogram; duration of the QRS complex
QT	QT interval of ECG, duration between the Q and T waves
QTc	QT interval of ECG corrected for heart rate
QTcB	QT interval of ECG corrected for heart rate using Bazett's formula
QTcF	QT interval of ECG corrected for heart rate using Fridericia's formula
RND	All Subjects Randomized
RR	Time duration between two consecutive R waves of the electrocardiogram
SAE	Serious Adverse Event
SAF	Safety Analysis
SAP	Statistical Analysis Plan
SAS	Simpson-Angus Scale
SAS®	Statistical Analysis Software
SCID-CT	Structured Clinical Interview for DSM Disorders - Clinical Trial Version
SD	Standard deviation
SDS	Sheehan Disability Scale
SMQs	Standard MedDRA Queries
SOC	System Organ Class
[REDACTED]	[REDACTED]
TEAE	Treatment-emergent adverse event
TOEPH	Heterogeneous Toeplitz structure
TOEP	Toeplitz structure
WHO	World Health Organization
YMRS	Young Mania Rating Scale

## 2. INTRODUCTION

This document describes the rules and conventions to be used in the presentation and analysis of efficacy, safety, [REDACTED] data for Protocol ITI-007-401. It describes the data to be summarized and analyzed, including specifics of the statistical analyses to be performed.

This statistical analysis plan (SAP) is based on protocol version 1.4, dated 09Mar2018. This SAP details analyses for the double-blind portion of the study (Part A) and only references the open label extension (OLE) where it pertains to the Part A analyses.

## 3. STUDY OBJECTIVES FOR PART A (DOUBLE-BLIND)

[figure not shown]
### 3.1. PRIMARY OBJECTIVE

The primary objective of Part A of this study is to compare the efficacy of 2 doses of ITI-007 administered orally once daily to that of placebo in mean change from baseline in the total score on the rater-administered Montgomery-Åsberg Depression Rating Scale (MADRS) in subjects with bipolar depression at Week 6.

## 3.2. SECONDARY OBJECTIVES

### 3.2.1. KEY SECONDARY EFFICACY

The key secondary objective of Part A of this study is to compare the efficacy of 2 doses of ITI-007 administered orally once daily to that of placebo in time to first response, defined as the number of days from first dose of study drug to the earliest date the patient experiences a sustained  $\geq 50\%$  reduction from baseline in the rater-administered MADRS total score.

**3.2.3. SECONDARY OBJECTIVES - SAFETY**

The safety objectives of Part A of this study are to determine the safety and tolerability of 2 doses of ITI-007 via change in the following safety endpoints:

- Incidence of adverse events (AEs);
- Young Mania Rating Scale (YMRS);
- Columbia Suicide Severity Rating Scale (C-SSRS);
- Abnormal Involuntary Movement Scale (AIMS);
- Barnes Akathisia Rating Scale (BARS);
- Simpson Angus Scale (SAS);
- Clinical laboratory evaluations;
- Electrocardiograms (ECGs);
- Vital sign measurements;
- Physical and neurological examination findings.

[REDACTED]

## 4. STUDY DESIGN

[figure not shown]

For more information, contact the Office of the Vice President for Research and Economic Development at [contact] or [[contact]](mailto:[contact]).

1

1 | Page

the *Journal of the American Statistical Association* (1955) and the *Journal of the Royal Statistical Society, Series B* (1956). The first of these papers was the first to propose the use of the  $\chi^2$  statistic for testing the hypothesis of no association in a two-way table. The second paper was the first to propose the use of the  $\chi^2$  statistic for testing the hypothesis of no association in a two-way table. The first of these papers was the first to propose the use of the  $\chi^2$  statistic for testing the hypothesis of no association in a two-way table. The second paper was the first to propose the use of the  $\chi^2$  statistic for testing the hypothesis of no association in a two-way table.

Black box with a white rectangular area for a logo or signature.

11. **What is the primary purpose of the *Journal of Clinical Endocrinology and Metabolism*?**

## 5.2. FINAL ANALYSIS

The analyses detailed in this SAP will be performed by [REDACTED] following [REDACTED] [REDACTED] this SAP, Database Lock, Sponsor authorization of Analysis Sets and Unblinding of Treatment.

---

## 6. ANALYSIS SETS

For Part A, analysis of efficacy and safety endpoints will be performed based on the analysis sets defined in this section and as specified for each endpoint throughout this SAP. [REDACTED]

[REDACTED] the inclusion/exclusion of subjects from each analysis set will be determined prior to the interim and final analyses (and approved by ITCI) based on blinded data review.

Note: Analysis sets defined in sections below are defined for Part A of the study.

### **6.1. ALL SUBJECTS ENROLLED [ENR] SET**

The All Subjects Enrolled (ENR) Set will contain all subjects who provide informed consent for this study.

### **6.2. ALL SUBJECTS RANDOMIZED [RND] SET**

The All Subjects Randomized (RND) Set will contain all subjects who signed informed consent and were randomized to study medication.

For analyses and displays based on RND, subjects will be classified according to randomized treatment.

### **6.3. INTENT-TO-TREAT [ITT] SET**

The intent-to-treat (ITT) Set will contain all randomly assigned subjects who receive at least one dose of study medication and who have a valid (pre-dose) baseline measurement and at least one valid post-baseline measurement of rater-administered MADRS total score. All analyses using the ITT Set will classify subjects according to randomized treatment, regardless of the treatment received during the course of the study. Note that the clinical study protocol refers to this population as the Efficacy analysis set (EAS).

[figure not shown]
[REDACTED] [REDACTED]

[REDACTED]

[REDACTED]

## **6.5. SAFETY ANALYSIS [SAF] SET**

The safety analysis (SAF) Set will contain all subjects who received at least one dose of study medication. All analyses using the SAF Set will classify subjects according to treatment actually received. In case of incorrect dosing, the treatment most often received will be taken as the actual treatment.

## **7. GENERAL CONSIDERATIONS**

Relative Study Day will be calculated from the date of Day 1, which is the day of first treatment with double-blind study medication in Part A, and will be used to show the start and/or stop days of treatment, study procedures and assessments, prior, concomitant, and post-treatment medications, and adverse events.

[figure not shown]
- If the date of the treatment, procedure, or event is on or after Day 1 date then:

Relative Study Day = (date of variable of interest – Day 1 date) + 1.

- If the date of the treatment, procedure, or event is prior to the Day 1 date then:

Relative Study Day = (date of variable of interest – Day 1 date).

In the situation where the date is partial or missing, Relative Study Day, and any corresponding event durations will appear missing in the listings.

Analyses presented by visit or study day will be based on the scheduled visits as planned in the protocol. Visit windows for unscheduled visits or early discontinuation visits are defined in **Table A**, which provides the mapping of relative day ranges to the scheduled target days and the study periods for Part A. If more than one assessment is available in the same ‘Range of Relative Study Days’ (window), the assessment closest to the Scheduled Target Day will be selected and assigned to the Scheduled Target Day. If two or more assessments are available in the same window and are equidistant from the Scheduled Target Day, the latest assessment will be selected (if before study Part B start). 

Listings will include scheduled, unscheduled, retest and early discontinuation data.

**Table A: Part A - Mapping of Relative Day Ranges to Schedule Target Day**

Study Phase	Study Period	Range of Relative Study Days	Scheduled Target Day	Scheduled StudyWeek
Pre-Treatment	Screening	1-14* days before Day 1 date	Day -14	-2
Pre-Treatment	Baseline	Day 1 date (definition of baseline varies by assessment – see descriptions below)	Day 1	0
Study Treatment	On-Treatment	2 to 11 days relative to Day 1 date	Day 8	1
Study Treatment		12 to 18 days relative to Day 1 date	Day 15	2
Study Treatment		19 to 25 days relative to Day 1 date	Day 22	3
Study Treatment		26 to 32 days relative to Day 1 date	Day 29	4
Study Treatment		33 to 39 days relative to Day 1 date	Day 36	5
Study Treatment		≥40 days relative to Day 1 date and after the last dose of treatment and before the start of the Safety Follow-up Period (one day after actual Day 43 visit) or Part B study.	Day 43	6
Post-treatment**	Safety Follow-up	> 43 days relative to Day 1 date for treatment completers (42 day on-treatment) and after Day 43 post-treatment assessments.	Day 57	8

\*\* Only for subjects not enrolling over into Part B study phase upon completing treatment in Part A.

First treatment with study medication and baseline assessments are scheduled for Visit 2 on Relative Study Day 1. For analysis purposes, baseline is defined as the last non-missing pre-treatment measurement and endpoint defined as the last Part A On-treatment measurement.

Assessments will be considered baseline if the assessment date is before the date of the first treatment of the 6-week On Treatment Period or if the assessment was done on Study Day 1 and, according to the Study Schedule of Events, was supposed to be performed on Day 1, prior to treatment. Bracket assessments originally scheduled for Day -1 that are rescheduled for Day 1 and are confirmed as taken prior to first dose will be considered baseline.

Unless otherwise specified, the following calculations will be used for change from baseline and percent change from baseline of quantitative measurements:

Change from baseline will be calculated as:

- Value at Visit X – Baseline Value

Percent change from baseline will be calculated as:

- $$\frac{\text{Value at Visit X} - \text{Baseline Value}}{\text{Baseline Value}} \times 100$$

All investigative sites with fewer than 6 ITT subjects will be pooled as follows: The largest site with fewer than 6 ITT subjects will be pooled with the smallest site with fewer than 6 ITT subjects. If this results in a pooled site still having fewer than 6 ITT subjects, this site will be pooled together with the next smallest investigative site, if one exists; otherwise, no further pooling is needed. Sites with the same number of ITT subjects will be ordered in ascending order of their numerical site identification number. This will serve as a tie-breaker rule in case multiple sites have the same number of ITT subjects. If the primary efficacy analysis model, described in [Section 15.1.3](#) presents convergence issues due to the too small number of subjects per site, the same site pooling algorithm will be applied again, but this time pooling sites with fewer than 12 ITT subjects. Should the primary efficacy analysis model still present convergence issues, after testing the sequence of correlation structures listed in [Section 15.1.3](#), then the site effect will be reconsidered and may be dropped from the model. These pooled investigative sites, as determined based on the primary efficacy response variable, will be used for any analysis that has investigative site as a fixed effect in the model. The actual investigative site numbers will be included in the listings.

The default significance level for statistical tests will be 5%; confidence intervals will be 95% and all tests will be two-sided, unless otherwise specified in the description of the analyses. All analyses will be conducted using SAS® version 9.4 or higher.

[figure not shown]
## 7.1. MISSING DATA

The total and subscale scores of any assessment with more than one item, such as rater-

[figure not shown]
administered MADRS, will be derived from individual items. Any individual missing item in any scale will not be imputed. If one or more items are missing at a visit, then the associated total score or subscale score will be set to missing.

The main objective of the analyses in Part A of this study is to evaluate the effect of ITI-007 compared to placebo if the treatment is administered for the planned study duration. In order to evaluate this estimand in the presence of subjects that may discontinue treatment prematurely, the primary efficacy analyses will be performed based on an assumption of data being missing at random (MAR). This implies that subjects discontinuing from treatment early are considered to have unobserved values similar to the observed ones in their treatment group for subjects who have similar history, i.e., the distribution of the unobserved future outcomes for subjects who had discontinued treatment is the same as the distribution of the observed outcomes for those who continued treatment, conditional on the available data prior to discontinuation.

The Mixed-Effects Model for repeated Measures (MMRM) will be used for the analysis of the primary efficacy endpoint in Part A. The MMRM approach does not impute missing data but is based on all subjects included in the analysis set using all available longitudinal data (either complete or partial). This approach is based on the MAR assumption as described above.

### **7.3. EXAMINATION OF SUBGROUPS**

The following subgroups will be assessed as part of the exploratory analyses for Part A:

- Bipolar I or Bipolar II;
- Severity of illness determined by MADRS score at Screening (Mild or Absent (score of 0 to 19), Moderate or Severe (score of 20 to 60));
- Age category ( $\leq 40$ ,  $> 40$  years);
- Gender;
- Race (White or Non-White);
- Ethnicity (Hispanic or Latino or Not Hispanic or Latino);
- Study Site;
- Age at first diagnosis ( $<22$ ,  $\geq 22$  years)

---

- Number of lifetime bipolar depressive episodes (1-9, 10-20, >20 episodes).

Other subgroup analyses may be performed as deemed appropriate.

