4.1 Selection of Study Population

Approximately 549 patients (183 patients/arm in Part A) will be enrolled at approximately 60 study sites in the United States. In Part A, patients will be randomly assigned to study treatment only if they meet all of the inclusion criteria and none of the exclusion criteria. In Part B, up to 549 patients who safely completed Part A may receive ITI-007 60 mg.

Deviations from the inclusion and exclusion criteria are not allowed because they can potentially jeopardize the scientific integrity of the study, regulatory acceptability, or patient safety. Therefore, adherence to the criteria, as specified in the protocol, is essential.

In Part A, appropriateness of patient eligibility will be assessed by expert site-based raters and investigators and confirmed by remote, independent expert raters and/or medical monitor(s) by a systematic adjudication process in concert with the sponsor. In Part B, appropriateness of patient eligibility will be assessed by the investigator. In the event of a recently emerged new medical condition, this should be evaluated carefully and discussed with the Medical Monitor prior to participation in Part B of the study. Once a final decision is made, no waivers for exceptions will be provided.

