4.1.1 Part A Inclusion Criteria

Each patient must meet all of the following criteria to be enrolled in this study:

1. Is capable of understanding the written informed consent, provides signed and witnessed written informed consent, and agrees to comply with protocol requirements.
2. Is between the ages of 18 and 75 years, inclusive, at the start of screening (both male and female patients are to be included).
3. Meets the Diagnostic and Statistical Manual of Mental Disorder, 5th Edition (DSM-5) criteria for Bipolar I or Bipolar II Disorder as confirmed by the investigator or sponsor-approved expert site-based rater by a Structured Clinical Interview for DSM-5 Disorders – Clinical Trials Version (SCID-5-CT) and meeting all of the following 5 criteria:

- a. The start of the current MDE is at least 2 weeks but no more than 6 months prior to the screening visit;
- b. Appropriate severity of illness, at least moderately ill, as measured by a rater-administered MADRS total score ≥ 20 and corresponding to a CGI-BP-S score of ≥ 4 at the screening and baseline visits;
- c. Sufficient history and/or independent report (such as family member or outside practitioner) verifying that the current MDE is causing clinically significant distress or impairment in social, occupational, or other important areas of functioning;
- d. A lifetime history of at least 1 bipolar manic episode or mixed episode (for Bipolar I) or hypomanic episode (for Bipolar II);
- e. A rater-administered YMRS total score of ≤ 12 at the screening and baseline visits. The presence of psychotic symptoms may result in an increased YMRS without evidence of mania/hypomania. Therefore, a patient with a YMRS > 12 AND psychotic symptoms may be included pending adjudication review for diagnostic certainty of the depressive episode.

4. Has a body mass index (BMI) of 18 – 35 kg/m², inclusive.
5. Either must agree to use highly effective methods of birth control (defined as those, alone or in combination, that result in a failure rate less than 1 percent per year when used consistently and correctly) for at least 2 weeks prior to randomization (starting with signing informed consent) through to the end-of-study follow-up visit or must be of non-childbearing potential (defined as either permanently sterilized or, if female, post-menopausal; the latter is defined as at least 1 year with no menses without an alternative medical explanation).

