7.4 Description of Subgroups to be Analyzed

Subgroup analyses of efficacy and safety variables may be conducted as deemed appropriate. For subgroup analyses using either MMRM or ANCOVA with LOCF, the corresponding subgroup terms will be added to the model: subgroup, subgroup-by-treatment, subgroup-by-visit, and subgroup-by-treatment-by-visit interactions. Subgroup analyses will be detailed in the SAP.

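### The severity subgroup in SAP 7.3 is cut at the trial's own entry limit (MADRS 20), so no eligible patient can fall in its lower category

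*SAP*

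**What the plan says.** SAP section 7.3 lists the subgroups to be examined in the exploratory Part A analyses. One is "Severity of illness determined by MADRS score at Screening", with the categories "Mild or Absent (score of 0 to 19), Moderate or Severe (score of 20 to 60". The section does not say whether the rater-administered or the computer-administered MADRS is meant.

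Protocol section 4.1.1, criterion 3b, sets the entry condition: "rater-administered MADRS total score ≥ 20 and corresponding to a CGI-BP-S score of ≥ 4 at the screening and baseline visits". The synopsis repeats it. Protocol section 4.1 makes it binding. It states that "patients will be randomly assigned to study treatment only if they meet all of the inclusion criteria and none of the exclusion criteria", that "Deviations from the inclusion and exclusion criteria are not allowed", and that after the final eligibility decision "no waivers for exceptions will be provided".

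Protocol section 7.4 describes how subgroups enter an MMRM or LOCF ANCOVA: "the corresponding subgroup terms will be added to the model: subgroup, subgroup-by-treatment, subgroup-by-visit, and subgroup-by-treatment-by-visit interactions". It leaves further detail to the SAP.

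**The concern.** The subgroup boundary and the entry limit are the same number, on the same scale, at the same visit. A two-level subgroup can show whether an effect differs between levels only if both are populated. Here the lower level can contain only patients who should not have been randomised.

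What is lost is the plan's one listed look at whether the effect varies with depression severity at entry; none of the other subgroups in SAP 7.3 measures it. The report would carry a severity row that duplicates the overall result. If a few eligibility violators fill the other row, it would also carry a contrast driven by them. A better cut chosen after unblinding would be post hoc.

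**Working it through.** **Design figures.** Protocol section 7.2 gives a 3-point difference, SD 7.5, overall two-sided 0.05 with a Bonferroni split over two doses (0.025 each), 90% power and 14% early discontinuation.

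- Normal approximation: n = 2(z₀.₉₈₇₅ + z₀.₉₀)² × 7.5²/3², which rounds up to 156 per arm.
- Noncentral t: power is 89.9% at 156 and 90.1% at 157, so the plan's 157 per arm is reproduced.
- Randomised: 157/0.86 = 182.6, so 183 per arm, and 3 × 183 = 549, as stated.

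These figures are not in dispute. They supply the SD and arm size used below.

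**Step 1: overlap of the entry range with the categories.** The MADRS total runs from 0 to 60 (protocol section 6.2.1).

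| Set of screening scores | Range | Eligible scores in it |
|---|---|---|
| Eligible under 3b | 20–60 | 41 of 41 |
| SAP lower category | 0–19 | 0 of 41 |
| SAP upper category | 20–60 | 41 of 41 |

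The upper category is the eligible population. The YMRS criterion (3e) has an adjudicated exception; 3b has none, so there is no legitimate route into the lower category.

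**Step 2: what the model can estimate.** Take a single visit with six columns: intercept, two treatment indicators, an indicator for the lower category, and its two products with treatment.

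- No patient in the lower category: the last three columns are all zero and the rank is 3 of 6. Neither the subgroup effect nor either interaction is estimable. Adding visit does not help, because the subgroup-by-visit and three-way columns are zero as well.
- One patient in the lower category, in one arm only: the rank is 4 of 6, and the two interaction terms are still not both estimable.

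**Step 3: a few patients randomised in error.** The ITT set in SAP section 6.3 does not remove eligibility violators, so the lower category could hold some. Their number is not known; the values of k below are assumptions. With k per arm in the lower category and 157 − k in the upper, the standard error of one dose's interaction with placebo is

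SE = 7.5 × √{2 × [1/k + 1/(157 − k)]}

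| k per arm (assumed) | Calculation | SE (points) |
|---|---|---|
| 1 | 7.5 × √[2(1/1 + 1/156)] | 10.6 |
| 2 | 7.5 × √[2(1/2 + 1/155)] | 7.5 |
| 5 | 7.5 × √[2(1/5 + 1/152)] | 4.8 |
| 78 (near-even split) | 7.5 × √[2(1/78 + 1/79)] | 1.7 |

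Even with five violators in every arm, the standard error exceeds the 3-point effect the trial is designed to detect. A near-even split of eligible patients would give about 1.7.

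**The case against.** Four points can be made for the plan.

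1. **It is exploratory.** The subgroup is one of nine listed, and nothing confirmatory depends on it. An empty row would be obvious in the output, and SAP 7.3 allows further subgroup analyses. This stands as a limit on importance. It does not repair the specified analysis, and a cut added later under that allowance would not be pre-specified.

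2. **The instrument is not named.** SAP section 15.1.1 mentions a computer-administered MADRS at screening, and the entry limit applies only to the rater's score. On that reading an eligible patient could score 0 to 19. But protocol section 6.2.1 starts the computer interview only after the screening visit, and nothing visible assigns that score to this subgroup. If it were intended, SAP 7.3 would still need to say so.

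3. **The interaction model is conditional.** Protocol 7.4 says subgroup analyses may be done and defers to the SAP, where the text of section 15.4.3.2 is redacted. The SAP may fit within strata instead. This limits what can be said about a failing interaction test. It leaves the empty category untouched, and a within-stratum fit would still have nothing to compare.

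4. **Empty by design is too strong.** It means empty among eligible patients; violators could appear. That is accepted, and Step 3 shows that a handful of them would carry almost no information.

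**Conclusion.** The concern holds. With the rater-administered score, which is the natural reading of SAP 7.3, the lower category contains 0% of eligible patients and the upper category 100%. The planned split therefore cannot show whether the treatment effect depends on severity. Any contrast that did appear would come from patients randomised in error, with a standard error of roughly 5 to 11 points for an assumed one to five per arm.

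This should be corrected, but it does not threaten the trial's main conclusions: the primary analysis, key secondary analysis, type I error control and sample size are unaffected. The finding rests on criterion 3b being enforced as protocol section 4.1 states, and on the redacted part of the SAP not redefining the subgroup.

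**What to change.** In SAP 7.3, state that the rater-administered MADRS is used and replace the 0–19 versus 20–60 split with one inside the eligible range, fixed before unblinding. Two workable choices are a fixed value and the median of the blinded, pooled baseline scores. Keeping the cut at 20 and switching from screening to baseline would not help, because 3b applies at both visits.

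Alternatively or in addition, report the treatment interaction with continuous baseline MADRS, which is already a covariate in the primary model (SAP section 15.1.3) and avoids choosing a cut. Basing the subgroup on baseline also aligns it with that model, though this is a preference; the defect itself requires only that the cut move or that the score be used as continuous.

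The cost is about one line in SAP 7.3, with matching edits to the table shells and to section 15.4.3.2 if it repeats the categories. No new data are needed.
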